7.6.4 Adverse Events Leading to Dose Modification

AEs leading to dose delay/reduction will be summarized by treatment group:

- Overall summary of AEs leading to dose delay/reduction by worst CTC grade (any grade, grade 3-4, grade 5) presented by SOC/PT.

- Overall summary of related AEs leading to dose delay/reduction by worst CTC grade (any grade, grade 3-4, grade 5) presented by SOC/PT.

The analysis will be conducted using the 30-day safety window.

A by-subject AEs leading to dose delay/reduction listing will be provided.

7.6.5 Adverse Events

Adverse events will be summarized by treatment group.

The following analyses will be conducted using the 30 days safety window only:

- Overall summary of any AEs by worst CTC grade (1, 2, 3, 4, 5, not reported, total) presented by SOC/PT.
- Overall summary of any AEs presented by worst CTC grade (any grade, grade 3-4, grade 5) by SOC/PT. This table will be restricted to events with an incidence greater or equal to 5% in any treatment group.
- Overall summary of any non-serious AEs presented by SOC/PT. This table will be restricted to events with an incidence greater or equal to 5% in any treatment group.
- Overall summary of any AEs that required immune modulating medication by worst CTC grade (any grade, grade 3-4, grade 5) presented by SOC/PT.
- Overall summary of drug-related AEs by worst CTC grade (1, 2, 3, 4, 5, not reported, total) presented by SOC/PT.

The following analyses will be conducted using the 30 days safety window and repeated using the 100 days safety window:

- Overall summary of drug-related AEs by worst CTC grade (any grade, grade 3-4, grade 5) presented by SOC/PT.

A by-subject AE listing will be provided. A by-subject listing of any AE requiring immune modulating medications will also be provided.

For those subjects treated in Arm B and for those intermediate/poor risk treated subjects in Arm A and Arm C:

The following analyses will be conducted using the 30 days safety window only:

- Overall summary of any AEs by worst CTC grade (1, 2, 3, 4, 5, not reported, total) presented by SOC/PT.
- Overall summary of any AEs that required immune modulating medication by worst CTC grade (any grade, grade 3-4, grade 5) presented by SOC/PT.
- Overall summary of drug-related AEs by worst CTC grade (1, 2, 3, 4, 5, not reported, total) presented by SOC/PT.

The following analyses will be conducted using the 30 days safety window and repeated using the 100 days safety window:

- Overall summary of drug-related AEs by worst CTC grade (any grade, grade 3-4, grade 5) presented by SOC/PT.

A by-subject AE listing will be provided. A by-subject listing of any AE requiring immune modulating medications will also be provided

7.6.6 Select Adverse Events (EU/ROW Submissions)

Unless otherwise specified, analyses will be performed by select AE category. Analyses will also be repeated by subcategory of endocrine events.

7.6.6.1 Incidence of Select AE

Select AEs will be summarized by treatment group for each category/subcategory.

The following analyses will be conducted using the 30-day safety window only:

- Overall summaries of any select AEs by worst CTC grade (any grade, grade 3-4, grade 5) presented by Category or Subcategory/PT.
- Overall summaries of any drug-related select AEs by worst CTC grade (any grade, grade 3-4, grade 5) presented by Category or Subcategory/PT.
- Overall summaries of any serious select AEs by worst CTC grade (any grade, grade 3-4, grade 5) presented by Category or Subcategory /PT.
- Overall summaries of drug-related serious select AEs by worst CTC grade (any grade, grade 3-4, grade 5) presented by Category or Subcategory /PT.
- Overall summaries of any select AEs leading to discontinuation by worst CTC grade (any grade, grade 3-4, grade 5) presented by Category or Subcategory /PT.
- Overall summaries of drug-related select AEs leading to discontinuation by worst CTC grade (any grade, grade 3-4, grade 5) presented by Category or Subcategory /PT.
- Summary of frequency of unique select AEs by Category.

A by-subject select AE listing will be provided.

7.6.6.2 Time-to Onset of Select AE

Time-to onset of drug-related select AEs (any grade, grade 3-5) will be summarized for each category/subcategory by treatment group.

Time-to onset analyses are restricted to treated subjects who experienced at least one drug-related select AE in the category/subcategory. The analyses will be conducted using the 30-day safety window.

Additional details regarding the time-to onset definition are described in time-to onset definition subsection of [APPENDIX 1](#).

7.6.6.3 Time-to Resolution of Select AE

Time-to resolution of the following specific events will be summarized separately for each category/subcategory.

- Time-to resolution of drug-related select AE (any grade, grade 3-5) by treatment group
- Time-to resolution of drug-related select AE (any grade, grade 3-5) where immune modulating medication was initiated, by treatment group

Time-to resolution analyses are restricted to treated subjects who experienced the specific events. Time-to resolution where immune modulating medication was initiated analyses are restricted to treated subjects who experienced the specific events and who received immune modulating medication during the longest select AE.

The analyses will be conducted using the 30-day safety window.

The following summary statistics will be reported: percentage of subjects with resolution of the longest select AE, median time-to resolution along with 95% CI (derived from Kaplan-Meier estimation) and ranges.

See time-to resolution definition subsection of [APPENDIX 1](#) for additional details.

7.6.7 Immune-Mediated Adverse Events (US Submission)

IMAEs will be summarized by treatment group for each immune-mediated category / PT using the 100-day safety window:

- Overall summary of non-endocrine IMAEs by worst CTC grade (any grade, grade 3-4, grade 5) where immune modulating medication was initiated presented by Category / PT.
- Overall summary of endocrine IMAEs by worst CTC grade (any grade, grade 3-4, grade 5) presented by Category / PT.
- Overall summary of non-endocrine IMAEs leading to discontinuation by worst CTC grade (any grade, grade 3-4, grade 5) where immune modulating medication was initiated presented by Category / PT.
- Overall summary of endocrine IMAEs leading to discontinuation by worst CTC grade (any grade, grade 3-4, grade 5) presented by Category / PT.
- Overall summary of non-endocrine IMAEs leading to dose delay or reduction by worst CTC grade (any grade, grade 3-4, grade 5) where immune modulating medication was initiated presented by Category / PT
- Overall summary of endocrine IMAEs leading to dose delay or reduction by worst CTC grade (any grade, grade 3-4, grade 5) presented by Category / PT.
- Summaries of time-to onset and time-to resolution of non-endocrine IMAEs where immune modulating medication was initiated presented by Category.
- Summaries of time-to onset and time-to resolution of endocrine IMAEs presented by Category.

A by-subject listing of IMAEs will be provided. By-subject listings of time-to resolution for longest IMAEs cluster (any grade and grade 3-5 in separate summaries) will also be provided. For new studies which collect investigator assessment of potential IMAE data, a by-subject listing of AEs considered as immune-mediated events per investigator but not qualified for IMAEs definition will also be provided.

In addition, for all nivolumab treated subjects who experienced at least one IMAE, the following data presentation will be provided:

- Summary of subjects who were re-challenged with nivolumab by IMAE category, with extended follow-up
- Summary of subjects who were re-challenged with nivolumab or ipilimumab by IMAE category, with extended follow-up

For these, re-challenge is considered to have occurred when last nivolumab and/or ipilimumab infusion was administered after the onset of an IMAE.

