7.4.1.1 Dose Delay Criteria for Nivolumab and Ipilimumab

In Arm A, nivolumab administration should be delayed, and in Arm B, both nivolumab and ipilimumab administration should be delayed, for any of the following:

- Any Grade ≥ 2 non-skin, drug-related AE, with the exception of fatigue
- Grade 2 drug-related creatinine, AST, ALT, and/or total bilirubin abnormalities
- Any Grade 3 skin, drug-related AE
- Any Grade 3 drug-related laboratory abnormality, with the following exceptions:
 - Grade 3 lymphopenia does not require dose delay
 - Grade 3 amylase or lipase abnormalities that are not associated with symptoms or clinical manifestations of pancreatitis do not require a dose delay.
 - Grade ≥ 3 AST, ALT or total bilirubin will require dose discontinuation (see section 8.1.1)
- Any adverse event, laboratory abnormality, or intercurrent illness which, in the judgment of the investigator, warrants delaying the dose of study medication.

During Cycles 1-4 in Arm B, both nivolumab and ipilimumab must be delayed at the same time.

Immuno-oncology agents, such as nivolumab and ipilimumab, are associated with AEs that differ in severity and duration than AEs caused by other therapeutic classes. Early recognition and management of AEs associated with immuno-oncology agents may mitigate severe toxicity. Management Algorithms have been developed to assist investigators in assessing and managing the following groups of AEs:

- Gastrointestinal
- Renal
- Pulmonary

- Hepatic
- Endocrinopathy
- Skin
- Neurological

The management algorithms recommended for use in CA2099ER are included in [Appendix 5](#).

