7.1.1 Adverse Events, Serious Adverse Events, Multiple events, Select Adverse Events, Other Events of Special Interest and Immune-Mediated Adverse Events

Drug-related AEs are those events with relationship to study drug “Related”, as recorded on the CRF. If the relationship to study drug is missing, the AE will be considered as drug-related.

Serious adverse events consist of AEs deemed serious by the Investigator and flagged accordingly in the CRF and clinical database.

Adverse events leading to study drug discontinuation are AEs with action taken regarding study drug(s) = “Drug was discontinued”.

Adverse events leading to dose delay are AEs with action taken regarding study drug(s) = “Drug was delayed”.

Adverse event that led to dose delay of the oral drug (similarly defined as dose omission or dose interruption) will be coded with action “Drug was interrupted”.

Adverse events leading to dose reduction are AEs with action taken regarding study drug(s) = “Dose was reduced”.

Adverse events will be coded using the Medical Dictionary for Regulatory Activities (MedDRA), and the most recent version of the dictionary at the time of the database lock will be used. Adverse events results will be graded for severity using NCI Common Terminology Criteria for Adverse

Events (CTCAE) and the most recent version of the criteria at the time of the database lock will be used.

In the AE summary tables, unless otherwise specified, subjects will be counted only once at the Preferred Term (PT), only once at the System Organ Class (SOC), and only once at subject level for the counting of total number of subjects with an AE. The AE tables will be sorted by the SOCs and then PTs. SOC will be ordered by descending frequency overall and then alphabetically. PTs will be ordered within SOC by descending frequency overall and then alphabetically. The sorting will be done based on the 'Any Grade' column of the experimental arm when arms are presented side-by-side.

Unless otherwise specified, the AE summary tables will be restricted to on-treatment events regardless of the causality.

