7.1.1.3 Immune-Mediated Adverse Events (US Submission)

In order to further characterize AEs of special clinical interest, analysis of immune-mediated AEs (IMAE) will be conducted. IMAEs are specific events (or groups of PTs describing specific events) that include pneumonitis, diarrhea/colitis, hepatitis, nephritis/renal dysfunction, rash, endocrine (adrenal insufficiency, hypothyroidism/thyroiditis, hypothyroidism, thyroiditis, hyperthyroidism, diabetes mellitus, and hypophysitis), and other specific events, considered as potential immune-mediated events by investigator that meet the definition summarized below:

- those occurring within 100 days of the last dose,
- regardless of causality,
- treated with immune-modulating medication (of note, endocrine AEs such as adrenal insufficiency, hypothyroidism/thyroiditis, hypothyroidism, thyroiditis, hyperthyroidism, diabetes mellitus, and hypophysitis are considered IMAEs regardless of immune-modulating medication use, since endocrine drug reactions are often managed without immune-modulating medication).
- with no clear alternate etiology based on investigator assessment, or with an immune-mediated component

The list of MedDRA preferred terms used to identify IMAEs is revisited quarterly and updated accordingly. The preferred terms used for the selection at the time of the database lock by categories will be provided.

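### SAP 7.6.7 counts participants as re-challenged even if nivolumab or ipilimumab was never held, so the re-challenge summaries mix uninterrupted treatment with true restarts

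*SAP*

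**What the plan says.** The re-challenge outputs are at the end of SAP 7.6.7. They are produced "for all nivolumab treated subjects who experienced at least one IMAE", and the first is described as "Summary of subjects who were re-challenged with nivolumab by IMAE category, with extended follow-up". A second summary does the same for nivolumab or ipilimumab. The operative rule is that "re-challenge is considered to have occurred when last nivolumab and/or ipilimumab infusion was administered after the onset of an IMAE".

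SAP 7.1.1.3 sets out what qualifies as an IMAE. Events are "those occurring within 100 days of the last dose", and they count "regardless of causality". Non-endocrine events must have been treated with immune-modulating medication, whereas endocrine events "are considered IMAEs regardless of immune-modulating medication use". There must also be no clear alternate cause in the investigator's assessment, or else an immune-mediated component. No minimum grade is set.

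Protocol 7.4.1.1 lists when nivolumab (and in Arm B ipilimumab) is to be delayed. For non-skin events the trigger is "Any Grade ≥ 2 non-skin, drug-related AE, with the exception of fatigue". For skin events it is a drug-related event of Grade 3. There are also criteria for laboratory abnormalities and a final criterion that leaves any other event to the investigator's judgment.

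**The concern.** A reader of a safety table will normally take re-challenge to mean that the drug was withheld because of an event and then given again. The protocol itself separates the two steps: 7.4.1 covers delay and 7.4.3.1 covers the criteria to resume. The SAP rule tests only the order of two dates, IMAE onset and last infusion. If some participants with an IMAE keep to their infusion schedule, the table reports them together with participants who stopped and restarted.

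At stake is the meaning of a reported count, by IMAE category, in a section headed as intended for the US submission.

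**Working it through.** The plan states no figure here, so there is nothing to reproduce. The check has three steps: read the rule, ask whether uninterrupted dosing after an IMAE is possible under the protocol, and see what can be said about size.

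**Step 1: conditions in the rule.** SAP 7.6.7 needs (i) an IMAE and (ii) a last infusion dated after its onset. It does not ask for a delay, for resolution or for a restart. No legible text elsewhere in either document adds such a condition. SAP 7.4.2.1 does define an actual nivolumab or ipilimumab delay (more than 3 days past the scheduled date), but 7.6.7 does not use it.

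**Step 2: can an IMAE occur without a hold?** Setting SAP 7.1.1.3 against Protocol 7.4.1.1:

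| Event | Can be an IMAE? | Met by the event-specific delay criteria? |
|---|---|---|
| Grade 1 endocrine event, no immune-modulating medication | Yes | No |
| Grade 1-2 skin event given immune-modulating medication | Yes | No |
| Event judged not drug-related, other IMAE conditions met | Yes | No |
| Drug-related Grade 2 or higher non-skin event (other than fatigue) | Yes, if other conditions met | Yes |

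In the first three rows a hold depends on the investigator's judgment. Arm A nivolumab is given every 2 weeks, so a participant with on-treatment onset who continues on schedule has the next infusion within 14 days and meets the rule. The rule also captures a participant whose event starts mildly, who receives the next scheduled infusion, and whose event then worsens so that nivolumab is stopped for good. That participant never restarted.

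**Step 3: size.** All inputs below are assumptions, because the documents give no IMAE, hold or restart counts.

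*Count.* Let H be participants infused after a hold for the IMAE and U those infused after onset with no hold. The reported count is H + U, so the excess is U. With u = U/(H + U), the reported count divided by H is 1/(1 − u):

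- u = 0.25: 1/0.75 = 1.33
- u = 0.50: 1/0.50 = 2
- u = 0.75: 1/0.25 = 4

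*How often a never-held participant is labelled re-challenged.* IMAEs count until 100 days after the last dose, and onset after the last infusion cannot satisfy the rule. Assume onset is uniform from first dose to last dose + 100 days, with T days from first to last nivolumab dose (1 month = 30.4375 days, SAP 8). The probability is T/(T + 100):

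- 3 months: 91.3/191.3 = 48%
- 6 months: 182.6/282.6 = 65%
- 12 months: 365.25/465.25 = 78.5%
- 24 months: 730.5/830.5 = 88%

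If a delay were required, the figure for a never-held participant would be 0% throughout.

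*Outcome rate, if one were reported.* With rate r_H in the held and r_U in the never-held, the pooled rate is u·r_U + (1 − u)·r_H. Take r_H = 30% and u = 0.50:

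- r_U = 5%: 2.5% + 15% = 17.5%
- r_U = 15%: 7.5% + 15% = 22.5%
- r_U = 30%: 15% + 15% = 30%
- r_U = 40%: 20% + 15% = 35%

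The pooled value can be below, equal to or above 30%, so the direction is not determined.

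**The case against.** The strongest reply is that this is a descriptive table with an openly stated definition, so a careful reader knows what is counted. Related information is also planned: SAP 7.6.7 tabulates IMAEs leading to dose delay or reduction and to discontinuation, and provides a by-subject IMAE listing; SAP 7.4.1 provides a by-subject dosing listing. Held and never-held participants could be identified from these. All of that is true, but none of the described outputs cross-classifies the re-challenged group by hold, so the summary itself cannot show how many were ever off drug.

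The never-held group is also narrower than the timing rule alone suggests. Non-endocrine IMAEs must have been treated with immune-modulating medication, events with a clear alternate cause and no immune component are excluded, and investigators may delay for any event. The management algorithms in Protocol Appendix 5 are not in the text available, so actual hold practice cannot be judged. These points limit the size of the group but do not empty it.

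Two stronger readings are tempting and should not be drawn. First, a reader might infer that the tables will make re-challenge look safer than it is, with a lower recurrence rate. SAP 7.6.7 names no recurrence rate or other outcome, SAP 9 leaves table mock-ups to the Data Presentation Plan, and the last calculation above shows that any bias could run either way. Second, a reader might infer that nearly every participant with an IMAE not requiring a hold will be labelled re-challenged. The 100-day window after the last dose argues against that: under the uniform-onset assumption the share is 48% at 3 months and 65% at 6 months.

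**Conclusion.** The point holds in limited form. As written, the SAP 7.6.7 rule combines uninterrupted treatment with true restarts and overstates the number re-challenged whenever at least one never-held participant is included. That conclusion needs only the wording of the rule and the fact that some qualifying IMAEs carry no mandated hold.

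The size of the overstatement is unknown. The factors of 1.33 to 4 rest on an assumed never-held share of 25% to 75%. The effect on any rate after re-challenge cannot be determined from the documents. PFS, OS, ORR and the AE incidence tables are untouched. This is a minor improvement, worth making because it changes what a submission table reports and is cheap.

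**What to change.** In SAP 7.6.7, split participants infused after IMAE onset into two rows, and do so in both re-challenge summaries:

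- (a) *Re-challenged*: infused after a nivolumab or ipilimumab delay attributed to that IMAE. The action taken for the infused drug must be recorded as delayed, and the delay must exceed 3 days under SAP 7.4.2.1.
- (b) *Continued without such a delay*: infused after onset, with (a) not met.

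Keep (a) + (b) as a third row, labelled *treated after IMAE onset*, for comparability with tables made under the present rule.

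The fields are already specified. SAP 7.1.1 records delay as an action taken and codes an AE-led delay of an oral drug separately as an interruption, which helps separate the infused drug from cabozantinib. SAP 7.4.2.1 takes the reason for delay from the CRF dosing pages.

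The cost is one derivation and the added rows. The group called re-challenged becomes smaller, so within-category numbers will be thinner. No dosing rule or data collection changes.

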7.6.8 Other Events of Special Interest

OEOSI will be summarized by treatment group for each category.

The following analyses will be conducted using the 100-day safety window:

- Overall summary of OEOSI by worst CTC grade (any grade, grade 3-4, grade 5) presented by Category / PT
- Overall summary of drug-related OEOSI by worst CTC grade (any grade, grade 3-4, grade 5) presented by Category / PT

A by-subject listing of OEOSI will be provided.

7.6.9 Multiple Events

The following summary tables will be provided:

- A table showing the total number and rate (exposure adjusted) of occurrences for all AEs.
- A table showing the total number and rate (exposure adjusted) of occurrences for AEs occurring in at least 5% of subjects in any treatment group.

In addition, the rate (exposure adjusted) and its 95% CI evaluated for different time intervals will be displayed graphically for each treatment group. This analysis will be limited to the rate of all AEs and all drug-related AEs. The analyses will be conducted using the 30-day safety window.

A listing displaying the unique instances of all AEs, i.e., after duplicates have been eliminated and overlapping and contiguous occurrences of the same event (i.e. same PT) have been collapsed will be provided. No formal comparisons will be made between treatment groups.

7.6.10 Laboratory Parameters

The analysis population for each laboratory test is restricted to treated subjects who underwent that laboratory test. Laboratory tests (in addition to the tests specified below) with CTC criteria collected in the specific studies may also be included in the summaries.

A by-subject listing of differences in categorization of SI and US laboratory test results will be provided.

7.6.10.1 Hematology

The following will be summarized by treatment group as worst CTC grade on-treatment per subject and as shift table of worst on-treatment CTC grade compared to baseline CTC grade per subject: hemoglobin (HB), platelets, white blood counts (WBC), absolute neutrophils count (ANC) and lymphocyte count (LYMPH).

The analyses will be conducted using the 30-day safety window.

A by-subject listing of these laboratory parameters will be provided.

7.6.10.2 Serum Chemistry

The following will be summarized by treatment group as worst CTC grade on-treatment per subject and as shift table of worst on-treatment CTC grade compared to baseline CTC grade per subject: ALT, AST, alkaline phosphatase (ALP), total bilirubin and creatinine.

The analyses will be conducted using the 30-day safety window.

A by-subject listing of these laboratory parameters will be provided.

